3.2.3 Study periods

[Table 3–1](#) shows which study periods are applicable to DE and LTFU subjects:

This document cannot be used to support any marketing authorization application and any extensions or variations thereof.
PUBLIC COPY

Table 3-1: Study periods

Period		Screening Period	Up-Titration Period			Evaluation Period							Down-Titration Period	Safety Period		
Subjects	Visit	ScrV	TV1	TV2	TV2	EV	MEV	FEV	MEV	FEV	MEV	YEV	...	FV/EDV	DTV	SV
			V1	V2	V3	V4	V5	V6	V7	...						
Subjects	DE	x	x	x	x	x	x	x	x	x	x	x	x	x	(x)	(x)
	LTFU					x	x	x	x	x	x	x	x	x	(x)	(x)
	Early Discontinuations												x	x	x	x

(x) – only applicable if the subject does not switch to another BRV study or is taking marketed drug after FV

The study is divided into 5 periods: Screening Period, Up-Titration Period, Evaluation Period, Down-Titration Period, and the Safety Period.

There is a Screening Period for all DE subjects. For DE subjects, this comprises assessments performed prior to the first dose of BRV in N01266. So start date of Screening Period is date of written informed consent and end date is the day before first dose of BRV (TV1-1). Although, patients in LTFU studies will not attend a screening visit, the screening information comprises information collected at various assessments during the core study and consequently will have been collected at different times depending on the domain. Domain specific information is detailed in Section 3.3.

The Up-Titration Period is only applicable to DE subjects, and the start date is the date of the first dose of BRV. The following algorithm is used to determine the end date:

- If the subject enters the Evaluation Period, the date 1 day prior to the EV is the end date
- If the subject does not enter Evaluation Period, the Up-Titration Period ends on the date of the final dose of BRV

For the Evaluation Period, the start date is the date of the first dose of BRV on or after the EV date, and the following algorithm is used to determine the end date:

- If the subject continues the study until it ends, the Evaluation Period ends on the date of FV
- If the subject prematurely discontinues the study, the date of EDV is the end date

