3.3 Definition of Baseline values

Baseline for all study outcomes will be determined using different methods depending on whether the subject is LTFU or DE.

Unless otherwise specified, Baseline values will be determined as follows:

- DE subjects: the last (most recent) available pre-dose measurement of the corresponding outcome will be used as Baseline
- LTFU subjects:
 - if available, Baseline values from the previous BRV core studies will be used as Baseline
 - otherwise the last (most recent) available measurement assessed between day of final on-treatment measurement in core study and the day before first BRV administration in N01266 will be used as Baseline

For laboratory parameters, vital signs (systolic blood pressure [SBP], diastolic blood pressure [DBP], and pulse rate), body weight, and ECGs, Baseline values will be determined as follows:

- DE subjects: the last (most recent) available pre-dose measurement of the corresponding outcome will be used as Baseline
- LTFU subjects: the last (most recent) available scheduled or UV assessment up to the day of subjects first BRV administration in core study will be used as Baseline (most recent measurement up to first BRV administration in core study, not in N01266 as in the general definition of Baseline values)

Baseline will be determined separately for each individual clinical laboratory parameter for hematology, biochemistry, endocrinology and urinalysis assessments.

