8.4 Vital signs, physical findings, and other observations related to safety

8.4.1 Vital signs

Vital signs, including measurements of blood pressure, supine or sitting pulse rate, and body temperature, are assessed after 5 minutes of rest at the ScrV, TV(s), and EV, MEV, FEV, YEV, FV, and at the EDV, Down-Titration Visit (DTV), and the SV in the case of early discontinuation. For LTFU subjects, at the EV, vital sign data will be obtained from the final visit of the core study (if available) and should not be recorded in the eCRF for N01266. If not available, vital signs data will be recorded within N01266 as for DE subjects.

Observed values and change from Baseline value for SBP, DBP, and pulse rate will be summarized for Baseline, EV, each visit during the Evaluation Period for which vital signs or body weight were assessed, EDV, Last Value on Treatment, FV, the Down-Titration Visit (DTV), and the Safety Visit (if available). This summary will be repeated separately for data collected during the Up-Titration visits for DE subjects.

The PCST criteria are based on FDA Division of Neuropharmacological Drug Products guidelines with some UCB-defined additions.

The number and percentage of subjects with any post-Baseline PCST value, any PCST low value, and any PCST high value will be summarized for SBP, DBP, pulse rate, and body weight. This summary will consider all assessments after the first dose of BRV and prior to or on the date of the final dose of BRV (excluding Up-Titration Assessments for DE Subjects). Percentages will be relative to the number of subjects with a post-Baseline assessment. This summary will be repeated for the Up-Titration Period for DE Subjects.

Additionally, the PCST table will be provided stratified by visit for all visits during Evaluation Period. Percentages will be relative to the number of subjects with a value at the corresponding visit.

A subject number table will be provided that identifies subjects with a clinically significant finding after the first dose of BRV for each type of vital sign abnormality.

All vital signs will be provided in subject data listings.

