8.4.2 ECGs

A standard 12-lead ECG is performed at the ScrV, TV(s), and EV, YEV, FV, and at the EDV in the case of early discontinuation. An ECG is performed at the SV only if the ECG results at the EDV are abnormal. At the EV, for LTFU subjects, ECG data will be obtained from the final visit of the core study (if available) and should not be recorded in the eCRF for N01266. If not available, ECG data will be recorded within N01266 as for DE subjects. The Investigator will determine whether the results of the ECG are normal or abnormal and assess the clinical significance of any abnormalities.

The number and percentage of subjects with no abnormality, an abnormal but not clinically significant finding, and a clinically significant finding will be summarized overall and by age group. This summary will consider all assessments after the first dose of BRV in the Evaluation and prior to or on the date of the final dose of BRV. Percentages will be relative to the number of subjects with a post-Baseline assessment in the Evaluation Period. This summary will be repeated for the Up-Titration Period for DE Subjects.

Additionally, this table will be provided stratified by visit for all visits during Evaluation Period. Percentages will be relative to the number of subjects with an ECG assessment at the corresponding visit. Subjects are counted only once at each time point based on the worst observed outcome across all abnormalities reported at that time point.

A subject number table will be provided that identifies subjects with a clinically significant finding after the first dose of BRV for each type of ECG abnormality.

All ECG data will be provided in subject data listings.

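### The overall vital-sign table in SAP 8.4.1 divides by subjects with any post-Baseline assessment, a wider group than the one whose values it counts

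*SAP*

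**What the plan says.** **Vital signs, SAP 8.4.1.** The scope of the overall PCST summary is "This summary will consider all assessments after the first dose of BRV and prior to or on the date of the final dose of BRV". A bracket then removes the Up-Titration values of DE subjects, and the denominator follows directly: "excluding Up-Titration Assessments for DE Subjects). Percentages will be relative to the number of subjects with a post-Baseline assessment". The summary is repeated for Up-Titration, with no denominator of its own. A by-visit version divides by subjects with a value at that visit.

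**Visits with vital signs, SAP 8.4.1.** They "are assessed after 5 minutes of rest at the ScrV, TV(s), and EV, MEV, FEV, YEV, FV, and at the EDV", and also at the Down-Titration Visit and the Safety Visit.

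**Baseline for vital signs and ECG, SAP 3.3.** For DE subjects: "DE subjects: the last (most recent) available pre-dose measurement of the corresponding outcome will be used as Baseline". For long-term follow-up (LTFU) subjects, the last "available scheduled or UV assessment up to the day of subjects first BRV administration in core study will be used as Baseline".

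**ECG, SAP 8.4.2.** The overall summary considers "all assessments after the first dose of BRV in the Evaluation and prior to or on the date of the final dose of BRV". Here the denominator does carry a period: "Percentages will be relative to the number of subjects with a post-Baseline assessment in the Evaluation Period".

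**Periods, SAP 3.2.3.** A DE subject who never enters the Evaluation Period has an Up-Titration Period that ends on the date of the final dose. For the Evaluation Period: "If the subject prematurely discontinues the study, the date of EDV is the end date".

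**The concern.** A percentage of subjects with an abnormal value should be taken over subjects who had a chance to show one in the window examined. In 8.4.1 the values considered are limited by dose dates and by period, while the denominator asks only for some assessment after Baseline. Children who contribute no eligible value can therefore still be divided by, and each of them lowers the percentage.

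The children most exposed to this are DE subjects who stop during Up-Titration. They belong to the Safety Set, which requires only one dose in this study (SAP 3.5.2). Long-term safety and tolerability is the primary objective, so even a small downward error in a safety percentage should be removed when the correction is this simple. The wording also leaves room for two programmers to produce different denominators from the same text.

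**Working it through.** The SAP states no percentage or count for this point, and SAP 2.4 says that no formal sample size calculation was made. There is no figure to reproduce. The check is a comparison of the rules, followed by an illustration.

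**Step 1: who can be in the numerator.** By SAP 3.2.1.1, first dose means the first dose in N01266, and final dose means the last dose across all periods. An eligible vital-sign value therefore lies after the first N01266 dose, on or before the final dose, and outside Up-Titration for DE subjects.

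**Step 2: who is in the denominator, read as written.** Any subject in the Safety Set with a vital-sign value after Baseline, from any period. Three groups meet this without an eligible value:

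- *DE subjects who leave during Up-Titration.* Dosing starts at the first Titration Visit (SAP 2.3.1) and Baseline is the last pre-dose value, so a value at a later Titration Visit is post-Baseline. Because Up-Titration then ends on the final dose date, their on-drug values are Up-Titration values and are excluded; anything later falls after the final dose.
- *LTFU subjects with only core-study values after Baseline.* Their Baseline precedes the first core-study dose, so the core study's final visit, which supplies the Entry Visit value, is already post-Baseline. This is rare, because vital signs are taken at every later visit and the first of these falls about 30 days after entry (SAP Table 2-1).
- *Subjects whose only post-Baseline values come after the final dose*, for example at the Safety Visit. This is also rare.

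**Step 3: the Up-Titration repeat.** A DE child may attend only the first Titration Visit and then the Entry Visit (SAP Table 2-1, footnote a). Up-Titration ends the day before the Entry Visit (SAP 3.2.3). If the Titration Visit value was pre-dose and there was no unscheduled visit, this child has no post-dose Up-Titration value, yet does have a post-Baseline value once measured in the Evaluation Period. The same gap applies.

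**Step 4: size.** Let N be the denominator as written and m the number of subjects in it without an eligible value.

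Shown % = matched % × (N − m) / N.

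Inputs: N = 100 (planned minimum of DE subjects) and N = 600 (planned total), both from SAP 2.4; m = 0, 5, 10, 20 and a matched rate of 10% are assumptions.

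| m | N = 100 | N = 600 |
|---|---|---|
| 0 | 10.0% | 10.0% |
| 5 | 10 × 95/100 = 9.5% | 10 × 595/600 = 9.9% |
| 10 | 10 × 90/100 = 9.0% | 10 × 590/600 = 9.8% |
| 20 | 10 × 80/100 = 8.0% | 10 × 580/600 = 9.7% |

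The relative loss is m/N: 5% to 20% in 100 subjects and 0.8% to 3.3% in 600, for m from 5 to 20.

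**Step 5: ECG for comparison.** The denominator in 8.4.2 is limited to the Evaluation Period, so DE subjects with ECGs only in Up-Titration are in neither count and add m = 0. What remains is a difference in end points. The values considered run to the final dose in any period, while the denominator runs to the end of the Evaluation Period. An ECG at an Early Discontinuation Visit (EDV) after the last dose can count only in the denominator, and an unscheduled ECG in Down-Titration can count only in the numerator.

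**The case against.** The strongest reply is that 8.4.1 never speaks of a numerator. Its scope sentence sets the data for the whole summary, so the post-Baseline assessment in the next sentence is naturally one of those the summary considers. Repeating the table for Up-Titration makes sense only if the denominator follows the table's scope, and SAP 3.1 says in general that denominators are chosen to suit the analysis. This reading is possible but not secure. Section 8.4.2 has the same kind of scope sentence and still adds the Evaluation Period to its denominator, 8.3 asks for an assessment on treatment, and both by-visit tables name their own denominator. The general sentence in 3.1 does not override a specific rule.

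Other parts of the reply stand. The primary variables are treatment-emergent adverse events and serious ones (SAP 2.2.1); vital signs and ECG are other variables (SAP 2.2.3). Section 8 names age group, seizure category and overall for the safety tables; a version for DE subjects alone rests on the general statement in Section 3. Up-Titration lasts at most 3 weeks, and nothing in the SAP says how many children leave during it. No abnormal value is lost, because Up-Titration has its own table and all vital signs are listed.

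A reader might also infer that the overall ECG table is diluted in the same way and that its three categories will fail to add to 100%. The SAP does not support this as a general statement. The ECG denominator already has a period limit. The EDV normally comes before the taper, and the final dose includes Down-Titration, so the EDV ECG of a child who tapers lies inside the window. SAP 3.2.3 does allow for subjects with no dose after the EDV, so a shortfall is possible, but only for those whose sole Evaluation Period ECG followed the last dose. The remaining mismatches run in both directions.

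**Conclusion.** The point holds for the overall vital-sign PCST table in 8.4.1 and its Up-Titration repeat. As written, the denominator admits subjects who cannot be counted as abnormal, and in the main table the effect is downward. The main group is DE subjects who leave during Up-Titration with a later Titration Visit value; the other two routes are rare.

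The size is small in the whole study and could be noticeable only in a DE-only table. It depends entirely on an assumed number of such children: if there are none, nothing changes. For 8.4.2 only a small difference in end points remains, and no direction or amount can be given for it. No test or error rate is involved. Severity: minor.

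**What to change.** In 8.4.1, state that percentages are relative to the number of subjects with at least one assessment of that parameter in the window the summary considers. For the Up-Titration repeat, state that the denominator is subjects with at least one post-dose assessment of the parameter within Up-Titration.

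In 8.4.2, as an alignment, give the assessments considered and the denominator the same end point: either the final dose for both or the end of the Evaluation Period for both.

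The cost is a sentence or two in each section and a change to the denominator flag. No data are removed, and affected vital-sign percentages in the main table become slightly higher.

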8.4.2 ECGs

A standard 12-lead ECG is performed at the ScrV, TV(s), and EV, YEV, FV, and at the EDV in the case of early discontinuation. An ECG is performed at the SV only if the ECG results at the EDV are abnormal. At the EV, for LTFU subjects, ECG data will be obtained from the final visit of the core study (if available) and should not be recorded in the eCRF for N01266. If not available, ECG data will be recorded within N01266 as for DE subjects. The Investigator will determine whether the results of the ECG are normal or abnormal and assess the clinical significance of any abnormalities.

The number and percentage of subjects with no abnormality, an abnormal but not clinically significant finding, and a clinically significant finding will be summarized overall and by age group. This summary will consider all assessments after the first dose of BRV in the Evaluation and prior to or on the date of the final dose of BRV. Percentages will be relative to the number of subjects with a post-Baseline assessment in the Evaluation Period. This summary will be repeated for the Up-Titration Period for DE Subjects.

Additionally, this table will be provided stratified by visit for all visits during Evaluation Period. Percentages will be relative to the number of subjects with an ECG assessment at the corresponding visit. Subjects are counted only once at each time point based on the worst observed outcome across all abnormalities reported at that time point.

A subject number table will be provided that identifies subjects with a clinically significant finding after the first dose of BRV for each type of ECG abnormality.

All ECG data will be provided in subject data listings.

8.4.3 Physical examination

A listing of abnormal physical examination findings will be provided; no summaries of physical examination findings are planned. Tanner scale will be recorded as part of the physical examination where applicable and will also be listed.

8.4.4 Neurological examination

A standard neurological examination is performed at the ScrV and EV (DE subjects only), FEV, YEV, FV, and at the EDV and the SV in the case of early discontinuation. For LTFU subjects, at the EV, neurological examination data will be obtained from the final visit of the core study and should not be recorded in the eCRF for N01266.

A listing of neurological examination findings will be provided; no summaries of neurological examination findings are planned.

8.4.5 Psychiatric and mental status

Psychiatric and mental status is reported by recording the presence or absence of psychiatric symptoms, mental impairment, and behavioral problems at the ScrV and EV (DE subjects only), FEV, YEV, FV, and at the EDV and the SV in the case of early discontinuation. For LTFU subjects, at the EV, psychiatric and mental status data is obtained from the final visit of the core study.

A listing of abnormal Psychiatric and Mental Status findings will be provided; no summaries of Psychiatric and Mental Status findings are planned.

8.4.6 Vagus nerve stimulation (VNS) status

VNS status is recorded at the ScrV, and EV (DE subjects only), MEV, FEV, YEV, FV and at the EDV and the SV. For LTFU subjects at the EV, VNS status is obtained from the final visit of the core study.

A listing of VNS status will be provided; no summaries of VNS data are planned (with the exception of VNS information recorded on medication pages, see section 6.4).

8.4.7 Neuro-imaging procedures

A brain MRI or brain CT scan (except in Germany) may be recorded prior to the date of the first dose of BRV and used as Baseline if no previous report was available within the 2 years prior to study entry into N01266. A listing of neuro-imaging findings will be provided; no summaries of neuro-imaging findings are planned. Neuro-imaging procedures are only applicable for LTFU subjects.

8.4.8 Assessment of suicidality

Suicidality is assessed by trained study personnel using the C-SSRS (Columbia-Suicide Severity Rating Scale) for subjects \geq 6 years of age. This scale will be used for screening as well as to assess suicidal ideation and behavior that may occur during the study.

Specific rules are provided to the study sites with regard to the identification of AEs or SAEs based on the outcome of this assessment. Because clinical events of interest will be recorded as AEs or SAEs, no study variable is defined for this assessment and no analyses are planned for the C-SSRS within the context of this study. However, subject data listings of the data for the C-SSRS will be provided. Additional listings will be provided for the subsets of subjects with suicidal ideation and the subset of subjects with actual suicide attempts

Suicide ideation includes a “yes” answer to any 1 of the 5 suicidal ideation questions on the C-SSRS:

- [REDACTED]
- [REDACTED]
- [REDACTED]
- [REDACTED]
- [REDACTED]

Suicide attempt includes response of a “yes” answer to any 1 of the 3 suicide attempt questions on the C-SSRS:

- [REDACTED]
- [REDACTED]
- [REDACTED]

8.4.9 Reproductive potential and birth control

A listing of reproductive potential and birth control measures for female as well as male subjects will be provided; no summaries of these findings are planned.

9 EFFICACY ANALYSES

All presentation for efficacy parameters will be based on the FAS and will be summarized by age group (<2 years and ≥ 2 years of age) and seizure category as categorized in Section 4.8, and overall.

Efficacy variables will be assessed using the seizure count information recorded on the DRC and EEG data. Endpoints derived from the DRC will be summarized separately from those derived from the EEG. EEG data collected from 24-hour EEG and 1-hour EEG will be presented separately.

Details of the derivations for all efficacy variables are provided in Section 3.10.3.1.

All summaries of efficacy data are descriptive; no statistical testing will be performed.

All seizure data and derived endpoints will be listed. Data from Up-Titration Period (DE subjects only) and Down-Titration Period will be listed only, if not otherwise mentioned.

9.1 Seizure based variables based on EEG data

EEG summaries will be presented by age group (< 2 years (24 hour EEG), ≥ 2 years (1 hour EEG)) and by seizure category. Outputs will explicitly restrict the analyses on 24 hour EEG to subjects < 2 years of age. If we have 1 hour EEG assessments for subjects categorized as < 2 years of age according to the Baseline age, we will perform sensitivity analyses in which we present results only by age group (< 2 years, ≥ 2 years), irrespective of the type of EEG performed. The POS and PGS* results for subjects ≥ 2 years will be missing, because EEG is only performed for subjects within Typical Absence seizure category there.

All analyses will be based on data assessed in Evaluation Period only.

Absolute and percent change in ADF will be summarized by age group and seizure category. Additionally, absolute and percent change in POS ADF will be summarized similarly.

Number of responders based on all seizure categories and the corresponding responder rate will be presented. Same will be presented for response based on POS only.

The number and percentage of seizure free subjects (Seizure freedom) will be presented.

Absolute and percent worsening based on PGS seizure types will be summarized.

All raw EEG seizure counts and derived efficacy variables will be listed.

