3.10.3.1 Derivation of efficacy variables

Efficacy variables will be assessed using the seizure count information recorded on the DRC and EEG data. Seizure count information will be evaluated over the Evaluation Period by 3-month periods based on the DRC (EV until EDV or FV). For DE subjects, seizure count information collected during the Up-Titration Period will be summarized separately. The EEG data will be reviewed at 6 months and yearly thereafter and presented by visit or by study period overall (no time interval presentations planned for EEG).

For subjects coming from core studies EP0065 and N01349 no EEG based values are available which can be obtained as Baseline for N01266. Consequently, these patients will be excluded from any efficacy analysis based on EEG data, where Baseline values are considered. If EEG is done in N01266 at any visit after Baseline, data should be used to assess any variables which do not require Baseline (e.g. seizure freedom).

Similarly, EP0065 and N01349 studies do not provide Baseline DRC data as compared to other core studies. EP0065 and N01349 subjects will be included/excluded in the planned analyses as per following table:

Table 3–6: Inclusion/Exclusion of EP0065 and N01349 data

Analysis	EP0065/N01349 included?
Absolute/percent change in ADF by EEG/	No
Absolute/percent change in 28-days adjusted (POS) seizure frequency by DRC	No
Responder Rate by EEG/ DRC	No
Absolute/percent worsening by EEG/ DRC	No
Seizure free days by DRC	Yes
Seizure freedom by EEG/ DRC	Yes
Average Daily Frequency	Yes (but not to be included in change from Baseline)
New incidence of seizure type	Yes

Calculations based on EEG data (LTFU subjects only)

EEG will be only analyzed for LTFU subjects. The Baseline EEG assessment to confirm POS seizures for DE subjects will not be used to derive efficacy variables. EEG assessments for subjects <2 years of age take 24 hours whereas for subjects ≥ 2 years of age with typical absence seizures only 1-hour EEG assessments were performed.

If the EEG interpretation is different based on EEG data from central reader and from site investigator (response captured in eCRF), then the site investigator interpretation is to be used. Please follow this table:

Table 3–7: EEG interpretation

	Site investigator interpretation = “normal”	Site investigator interpretation = “abnormal”
Central reader interpretation = “Normal”; 0 seizure counts	No problem	Use “Abnormal” with missing counts: ADF missing

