Central reader interpretation = “Abnormal”; >0 seizure counts	Use “Normal”; 0 counts	No problem

Calculation of average daily frequency (ADF) of seizures

Average daily frequency (ADF) of seizures based on the EEG data (from central reader or eCRF) is calculated differently for 1-hour and 24-hour EEG:

For 1-hour EEG:

$$\text{ADF} = \text{Number of seizures from EEG data source considered for 1 hour EEG} \times 24$$

For 24-hour EEG (with missing information on interpretable hours):

$$\text{ADF} = \text{Number of seizures from EEG data source considered for 24 hour EEG}$$

For 24-hour EEG (with information on interpretable hours):

$$\text{ADF} = \frac{\text{Number of seizures from EEG data source considered for 24 hour EEG}}{\text{Number of interpretable hours}} \times 24$$

The ADF will be calculated including all seizure types and additionally for POS seizures and PGS seizures, separately.

For certain endpoints, multiple EEG assessments are to be combined. In this instance, for n assessments, average ADF is given as:

$$\text{Average ADF} = \frac{\sum_{i=1}^n \text{ADF}_i}{n}.$$

Calculation of absolute change/worsening in ADF of seizures

Absolute change in ADF is calculated as:

$$\text{Absolute Change in ADF} = \text{Baseline ADF} - \text{postBaseline ADF}.$$

Both absolute changes will be calculated, with ADF including all seizure types and additionally based on POS seizures only.

Absolute worsening in PGS ADF is calculated as:

$$\text{Absolute Worsening in PGS ADF} = \text{postBaseline PGS ADF} - \text{Baseline PGS ADF}.$$

Calculation of percent change/worsening in ADF of seizures

Percent change in ADF is calculated as:

$$\text{Percent Change in ADF} = \frac{\text{Absolute Change in ADF}}{\text{Baseline ADF}} \times 100.$$

Both percent changes will be calculated, with ADF including all seizure types and additionally based on POS seizures only.

Percent worsening in PGS ADF is calculated as:

$$\text{Percent Worsening in PGS ADF} = \frac{\text{Absolute Worsening in PGS ADF}}{\text{Baseline PGS ADF}} \times 100.$$

Calculation of response

Response is defined to be equal to 1 for Percent Change in ADF $\geq 50\%$ and 0 for $< 50\%$. Both responses will be calculated, with percent change in ADF including all seizure types and additionally based on POS seizures only.

For subjects < 2 years of age response is based on the 24-hour EEGs performed over the Evaluation and Down-Titration Period separately.

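### The conditional EEG sensitivity analysis for children under 2 pools 1-hour with 24-hour recordings, which inflates the 50% responder rate, median percent change and EEG seizure freedom when nothing has changed (minor point)

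*SAP*

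**What the plan says.** SAP Section 3.10.3.1 sets the planned recording length: "EEG assessments for subjects <2 years of age take 24 hours", while children of 2 years or more with typical absence seizures have 1-hour EEGs. Section 9 keeps the two types in separate presentations, and Section 9.1 restricts the 24-hour analysis to children under 2.

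Section 9.1 then adds a contingency. "If we have 1 hour EEG assessments for subjects categorized as < 2 years of age according to the Baseline age", the sponsor will run "sensitivity analyses in which we present results only by age group (< 2 years, ≥ 2 years), irrespective of the type of EEG performed".

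The formulas that would feed that analysis are in Section 3.10.3.1:

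- 1-hour EEG: ADF is the "Number of seizures from EEG data source considered for 1 hour EEG", times 24.
- 24-hour EEG: ADF is the "Number of seizures from EEG data source considered for 24 hour EEG", rescaled by interpretable hours when these are known and left as the raw count when they are not.
- Several EEGs: "For certain endpoints, multiple EEG assessments are to be combined. In this instance, for n assessments, average ADF is given as" the sum of the ADF values divided by n. The endpoints concerned are not named.
- Response: "Response is defined to be equal to 1 for Percent Change in ADF" of at least 50%, where a positive change is a reduction.
- EEG seizure freedom: no EEG in the period shows a seizure. No minimum recording length is set.

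For children under 2, the same section bases response and seizure freedom on 24-hour EEGs. The sensitivity analysis departs from that and gives no replacement rule on weighting, minimum length or matching of Baseline and follow-up.

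**The concern.** Multiplying a 1-hour count by 24 gives an ADF that can only be 0, 24, 48 and so on. At rates that a 24-hour EEG picks up easily, most 1-hour EEGs are blank. Two separate routes follow.

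- **A 1-hour EEG standing alone at follow-up.** A blank recording scores ADF 0, a 100% reduction, whatever the Baseline. No averaging is involved; the ×24 scaling of one hour does it.
- **A 1-hour EEG averaged with a 24-hour EEG.** One hour gets the same weight as 24 hours, so a blank hour halves the combined ADF.

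Percent change in ADF (for POS) and the 50% responder rate are secondary variables for this age group (Section 2.2.2). A sensitivity table should show whether they are robust. If recording length alone moves the responder rate this far, neither agreement nor disagreement with the main table can be interpreted.

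**Working it through.** The SAP states no figure for this analysis, so there is none to reproduce. The check applies its formulas first to one child and then to simulated children whose seizure rate does not change.

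**One child, 24-hour Baseline ADF = 10**

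| Follow-up | ADF | Percent change | Responder? |
|---|---|---|---|
| Blank 1-hour EEG only | 24 × 0 = 0 | (10 − 0)/10 = 100% | Yes |
| 24-hour EEG with 10, plus blank 1-hour EEG, simple mean | (10 + 0)/2 = 5 | (10 − 5)/10 = 50% | Yes, just |
| The same two EEGs, weighted by hours | 24 × 10/25 = 9.6 | (10 − 9.6)/10 = 4% | No |
| 1-hour EEG with one seizure | 24 × 1 = 24 | (10 − 24)/10 = −140% | No |

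**Null model**

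Assumptions, none of them from the SAP: Poisson counts, a constant true rate d per day, and a 24-hour Baseline with at least one seizure. The SAP gives no seizure rates, so a range is shown. The follow-up count is Poisson(d) on a 24-hour EEG and Poisson(d/24) on a 1-hour EEG. At least 1,000,000 draws were made per rate.

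Share of children scored as 50% responders with no true change:

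| Rate/day | 24-hour follow-up | Single 1-hour follow-up | Simple mean of one of each | Weighted by hours |
|---|---|---|---|---|
| 3 | 28% | 88% | 54% | 26% |
| 6 | 16% | 78% | 44% | 14% |
| 12 | 6% | 61% | 33% | 5% |
| 24 | 1% | 37% | just under 20% | 1% |

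The single 1-hour column is essentially the chance of a blank hour, exp(−d/24). At 6/day that is exp(−0.25) = 78%. One seizure in the hour already needs a Baseline of 48 or more to count as response.

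**Other statistics under the same model**

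- Median percent change, 24-hour Baseline to a single 1-hour EEG: 100% at 3, 6 and 12/day, and 8% at 24/day.
- Seizure freedom where the only EEG in the period is 1 hour long: 88%, 78%, 61% and 37% are blank at 3, 6, 12 and 24/day. For a 24-hour EEG the chance is exp(−d): 5% at 3/day and 0.25% at 6/day.
- Mean percent change: about −30% at 3/day, −25% at 6/day and −10% at 12/day, the same whether follow-up is 24-hour, 1-hour or the mean of both.
- Mean absolute change at 6/day: between 0.00 and 0.02 seizures/day for all three follow-up types.

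The means do not move because 24 times a 1-hour count is an unbiased estimate of the daily rate. Its many zeros are balanced by occasional values of 24 or more.

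**The case against.** A reader might infer that the whole sensitivity analysis is biased towards benefit. The documents do not support that. Section 3.1 has both mean and median reported for continuous variables, and the means are not shifted. Only the responder rate, the median percent change and seizure freedom are. For seizure freedom the distortion arises where 1-hour EEGs stand in place of 24-hour ones; adding a 1-hour EEG to a 24-hour one cannot raise it.

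A reader might also infer that the SAP expects 1-hour EEGs in this age group, or that the main EEG results are affected. Section 9.1 is worded as a condition, the main tables keep EEG types apart, and all raw counts and derived variables are listed. Children from EP0065 and N01349 are already left out of the EEG change and response analyses, though Table 3-6 keeps them in seizure freedom.

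Equal weighting is not the whole explanation either. It matters only where EEGs are averaged, and Section 3.10.3.1 also plans by-visit presentation, where the ×24 scaling acts alone. Weighting by hours therefore does nothing for a lone 1-hour follow-up.

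These points limit the reach and the weight of the concern. They do not remove the mechanism, which follows from the stated formulas. That efficacy is exploratory (Section 2) and untested (Section 9) argues for a low priority, not for leaving a table that cannot be read.

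**Conclusion.** The point holds, as a minor one. If the contingency in Section 9.1 is triggered, the stated rules give a responder rate, a median percent change and an EEG seizure freedom rate that depend on recording length. At an assumed 6 seizures/day, null response rises from 16% to 78% for a single 1-hour follow-up and to 44% for the simple mean.

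The sizes rest on the Poisson model, on the assumed rates and on a 24-hour Baseline above zero. They describe an affected child. The effect on the reported percentages cannot be sized, because the number of children under 2 with 1-hour EEGs is not given.

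**What to change.** Amend Section 9.1, with one formula in Section 3.10.3.1, for this sensitivity analysis only:

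1. Where EEGs are combined, compute ADF as 24 × (total seizures)/(total interpretable hours). Count 24 hours for a 24-hour EEG whose interpretable hours are missing, as the existing formula for that case already implies.
2. For children under 2, report percent change, response and seizure freedom only when the follow-up includes a 24-hour EEG. For change and response, require a 24-hour Baseline as well.
3. List the other 1-hour EEGs in this age group without summarising them.

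Requiring only that Baseline and follow-up have equal length would not be enough: a 1-hour/1-hour pair with a Baseline above zero gives 80% null response at 6/day and 68% at 12/day. Nor would requiring 24 hours at follow-up alone: with a 1-hour Baseline above zero, null response at 6/day is 99%.

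The cost is SAP wording and one formula, with no new data. A few subjects may drop from the change, response and seizure-freedom rows of the sensitivity table, which then no longer covers every EEG regardless of type.
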